14.2 Phase 1 Dose De-Escalation Scheme

Within each study arm (newly diagnosed and relapsed/refractory) and within each randomization group (sequential and concurrent decitabine) start with dose Level 1 and evaluate 6 patients:

- a) If 0 or 1 patients have DLT, expand cohort to 12 patients; if ≤3 DLTs are observed in 12 patients declare Level 1 = Recommended phase 2 dose (RP2D) for that study arm and randomization group.
- b) If more than 1 of 6 or 3 of 12 patients have DLT with dose Level 1, enroll a cohort of 6 patients at dose Level -1.
- c) If 0 or 1 patients have DLT, expand cohort to 12 patients; if ≤ 3 DLTs are observed in 12 patients declare Level -1 = MTD for that study arm and randomization group.
- d) If more than 1 of 6 or 3 of 12 patients have DLT with dose Level -1, enroll a cohort of 6 patients at dose Level -2.
- e) If 0 or 1 patients have DLT, expand cohort to 12 patients; if ≤ 3 DLTs are observed in 12 patients declare Level -2 = MTD for that study arm and randomization group.
- f) If dose level -2 is found too toxic, the study will terminate for that study arm and randomization group.

Observed versus true DLT rates are summarized here, with two-sided confidence intervals (CIs) for probability of DLT with n=12 patients:

Observed DLTs	80% CI	90% CI
0 of 12 (0%)	(0%, 17%)	(0%, 22%)
1 of 12 (8%)	(0%, 29%)	(0%, 34%)
2 of 12 (17%)	(5%, 39%)	(3%, 44%)
3 of 12 (25%)	(10%, 48%)	(7%, 53%)
4 of 12 (33%)	(15%, 56%)	(13%, 61%)
5 of 12 (42%)	(22%, 64%)	(18%, 68%)

Note that 3 DLTs / 12 patients are permitted to declare MTD; if >3 DLTs are seen, dose reduction must occur.

In Phase 2, we use the term Recommended phase 2 dose (RP2D) to denote the dose level determined in Phase 1 to be used in Phase 2.

14.3 Phase 2

The primary objective of Phase 2 is to evaluate the rate of MRDneg CR after up to 2 courses of induction chemotherapy. We will also continue to evaluate toxicity during Phase 2.

A Simon Minimax two-stage design will be used. The historic rate of MRDneg CR with G-CLAM alone is 71%. Our regimen will be considered of no further interest if the true rate of MRDneg CR is 65% or less (null), while an MRDneg CR rate of 80% will be of considerable interest (alternative). The design has a one-sided type-1 error rate of 10% and a power of 80% for the primary outcome. Patients treated at the RP2D in Phase 1 will be included for assessment in Phase 2.

The first stage will evaluate 19 patients. If 13 or more patents achieve MRDneg CR, the trial will move to stage 2. Additionally, as we are targeting DLT <33% in Phase 1, if 7 or more of the first 19 patients (36%) have what would qualify as a DLT in cycle 1, we would suspend the study and consider closure or dose reduction. Under the null hypothesis of an MRDneg CR rate of 65%, the probability we stop accrual after the first stage is 51%.

The second stage would evaluate an additional 22 patients (total n=41). If 31 or more of these 41 patients achieve MRDneg CR and if 13 or fewer (<31%) have what would qualify as a DLT in cycle 1, we would consider the regimen worthy of further investigation.

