This protocol initially called for multiple cycles of decitabine in combination with chemotherapy: patients who failed to achieve CR without measurable residual disease (MRD), or MRDneg CR, were eligible for a 2nd cycle of decitabine + GCLAM, while those who did achieve this outcome were eligible for consolidation with decitabine + GCLA. Review of outcomes from the 4 ND patients who received on-protocol consolidation showed that 2 had delayed or absent recovery of neutrophils and platelets not related to leukemia, or morphological leukemia-free state (MLFS). Although it is difficult to interpret results from so few patients, in light of results from RR patients showing higher rates of MLFS than we would normally expect, we opt to restrict patients to a single cycle of decitabine in combination with GCLAM. Patients achieving MRDneg CR have the option of receiving GCLA consolidation (which is a standard therapy that they could receive on or off protocol), while those who do not achieve MRDneg CR will be taken off study. Because we recognize MLFS as a concern with this regimen, we will add criteria to the stopping rules to include bone marrow aplasia.

Rationale for adding a Phase 2 expansion cohort

Based on the 6 ND patients who have had their responses assessed, the combination of decitabine for 10 days and GCLAM appears to be effective. Within our first cohort of 6 patients, we had 1 DLT (a patient experienced early death), but responses in the other 5 patients showed MRDneg CR. Without an expansion cohort, we only have room to enroll another 4 patients on

Protocol 9713.00

the trial to determine the MTD or recommended Phase 2 dose (RP2D) assuming that the remaining patients have only 0 or 1 DLT. Because of these promising early results, we plan to expand our study in ND patients at the MTD/RP2D. The Phase 2 expansion includes stopping rules for both efficacy and safety.

2.0 **OBJECTIVES**

2.1 Primary Objective

- **2.1.1** Estimate the maximum tolerated dose (MTD) of decitabine when used concomitantly with G-CLAM in patients with newly diagnosed AML and highrisk MDS.
- **2.1.2** Compare, within the limits of a phase 1/2 study, the rate of complete remission without measurable residual disease (MRDneg CR) with decitabine + G-CLAM at the MTD compared to similar patients treated previously with G-CLAM alone.

2.2 Secondary Objectives

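### Objective 2.1.2 compares MRDneg CR with historical G-CLAM (71%), but the only efficacy rule in section 14.3 tests 65% and no analysis against 71% is specified

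*Combined protocol and SAP*

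**What the plan says.** All references are to the combined protocol and SAP.

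- **Objective 2.1.2** (primary): "Compare, within the limits of a phase 1/2 study, the rate of complete remission without measurable residual disease", against similar patients previously given G-CLAM alone.
- **Section 8.5** names MRDneg CR against G-CLAM historical controls as the Phase 2 primary endpoint, calls this the primary outcome comparison, and takes the best response over up to two induction cycles.
- **Section 10.0** gives comparison with the institution's past G-CLAM patients as the purpose of the 41 patients.
- **Section 14.3** words the aim differently: "The primary objective of Phase 2 is to evaluate the rate of MRDneg CR after up to 2 courses of induction chemotherapy". It then gives the benchmark, "The historic rate of MRDneg CR with G-CLAM alone is 71" percent, and sets the hypotheses: "Our regimen will be considered of no further interest if the true rate of MRDneg CR is 65% or less (null"), with 80% as the alternative. On error rates: "The design has a one-sided type-1 error rate of 10% and a power of 80% for the primary outcome".
- **The rule in 14.3** is a Simon minimax design. It continues if at least 13 of the first 19 respond. At the end it needs at least 31 responders among the 41, and it adds a DLT condition that carries the conclusion: "if 13 or fewer (<31%) have what would qualify as a DLT in cycle 1, we would consider the regimen worthy of further investigation".

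After the 71% is given, section 14 does not use it again. It contains no estimate, interval or test against that figure.

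**The concern.** Whether the rate exceeds 65% and how it compares with the 71% seen on G-CLAM alone are two different questions. Three sections name the second as the primary outcome; section 14.3 gives a rule only for the first. Because the null lies 6 points below the benchmark, a regimen to which decitabine adds nothing falls between the null and the alternative, and the plan does not say how the rule behaves there.

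What is at stake is the reporting of a primary objective. A pass supports a rate above 65% and further study. It leaves 2.1.2 unanswered, and the plan does not fix what will be reported for it. The form of that comparison, including the confidence level, would remain to be chosen once the data are known.

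**Working it through.** **Inputs (section 14.3).** Null 65%, alternative 80%, one-sided error 10%, power 80%; first stage 19 patients, continue at 13 or more; second stage 22 more, total 41, success at 31 or more; stated early-stopping probability under the null 51%; historical G-CLAM rate 71%, with no denominator, so treated here as fixed. DLT limits: suspend at 7 or more of 19; at most 13 of 41 at the end.

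**Step 1. Reproduce the plan's figures.** With X1 ~ Bin(19, p) and X2 ~ Bin(22, p):

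P(pass) = Σ (x = 13 to 19) P(X1 = x) · P(X2 ≥ 31 − x)

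P(early stop) = P(X1 ≤ 12)

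| True rate p | P(early stop) | P(efficacy criterion met) |
|---|---|---|
| 65% | 0.519 | 0.0960 |
| 71% | 0.299 | 0.3091 |
| 80% | 0.068 | 0.8002 |

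The 10% error, the 80% power and (within a point) the 51% early stop are confirmed. An exhaustive search for the minimax design with these error limits also returns 13/19 and 31/41. The design is correct for the hypotheses it states.

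**Step 2. The rule at the benchmark.** The middle row is what the plan does not give: at G-CLAM's own rate the efficacy criterion is met 30.9% of the time. This is a design-stage figure, before any outcomes are known. Section 14.3 also says "Patients treated at the RP2D in Phase 1 will be included for assessment in Phase 2"; the effect of outcomes already seen is a separate matter and is not in this figure.

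**Step 3. Add the DLT limits.** The documents give no expected DLT rate q, so q is assumed. DLT and response are taken as independent, and 7 or more DLTs in 19 is treated as a stop.

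P(DLT limits met) = Σ (x = 0 to 6) P(D1 = x) · P(D2 ≤ 13 − x), with D1 ~ Bin(19, q) and D2 ~ Bin(22, q)

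| Assumed q | P(DLT limits met) | Full rule met at 71% |
|---|---|---|
| 20% | 0.922 | 0.3091 × 0.922 = 0.285 |
| 25% | 0.777 | 0.3091 × 0.777 = 0.240 |
| 30% | 0.549 | 0.3091 × 0.549 = 0.170 |

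**Step 4. What passing results say about 71%.** Exact (Clopper-Pearson) two-sided 80% intervals, unadjusted for the two stages:

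| Responders | Estimate | 80% interval | Contains 71%? |
|---|---|---|---|
| 31/41 | 75.6% | 64.9% to 84.3% | yes |
| 32/41 | 78.0% | 67.6% to 86.3% | yes |
| 33/41 | 80.5% | 70.2% to 88.3% | yes |
| 34/41 | 82.9% | 73.0% to 90.2% | no |

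Adjusting for the two stages moves 31/41 only to 65.2% to 84.4%. At the 90% and 95% levels the first counts to exclude 71% are 35/41 (lower limit 73.2%) and 36/41 (73.8%).

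**Step 5. How often a pass lands at 31 to 33.** P(X1 ≥ 13 and total ≥ 34) is 0.0603 at 71% and 0.4066 at 80%.

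- At 71%: 0.3091 − 0.0603 = 0.2488, and 0.2488 / 0.3091 = 80% of passes.
- At 80%: 0.8002 − 0.4066 = 0.3936, and 0.3936 / 0.8002 = 49% of passes.

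So a pass whose interval still contains 71% is a likely result even for a regimen at the alternative.

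**The case against.** The strongest reply is that the plan is a coherent screening design. It states its 65% null openly, places 65% and 80% either side of the quoted 71%, hedges objective 2.1.2 by the limits of a phase 1/2 study, and words a pass only as making the regimen worth further investigation. On that reading the bracketing is itself the limited comparison, and the pass probability at a value between null and alternative is helpful but optional.

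Much of this stands. A null below the historical rate is legitimate, and the stated error and power are right. Endpoint, response window, cut-offs and sample size are all prespecified. The hedge, however, limits how strong the comparison can be; it does not say what the comparison is.

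Three stronger readings are tempting and are not supported:

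- A reader might take 30.9% as an inflated type-1 error. It is not. The 10% is defined at 65%, and 71% lies outside the stated null.
- A reader might take 30.9% as the chance of a full pass. It covers the efficacy criterion alone; the DLT limits lower it.
- A reader might infer that the plan claims a pass shows superiority to G-CLAM. No section says so.

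**Conclusion.** The point holds as a gap between a stated primary objective and the specified analysis. It is not an error in the design's arithmetic. Followed as written, section 14.3 can support a rate above 65%, but it cannot answer 2.1.2. At the design stage a regimen equal to G-CLAM meets the efficacy criterion 30.9% of the time, or about 28%, 24% and 17% for the full rule at assumed DLT rates of 20%, 25% and 30%. The three lowest passing counts do not exclude 71% at the 80% level.

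These figures rest on 71% being a fixed constant and, for the full rule, on independence of response and DLT. Because no denominator is given for 71%, neither its sampling error nor the similarity of the historical patients is covered. The exclusion counts of 34, 35 and 36 are therefore firmer on paper than in fact. The matter should be clarified.

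**What to change.** Leave cut-offs and sample size as they are, and change the wording.

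- **(a) Section 14.3:** beside the 10% at 65%, state the design-stage probability of meeting the efficacy criterion at 71% (about 31%).
- **(b) Sections 14.3, 2.1.2 and 8.5:** state that meeting the rule by itself supports only a rate above 65% and further study, and does not by itself show improvement over G-CLAM.
- **(c) Analysis for 2.1.2:** specify the MRDneg CR estimate with an exact confidence interval, at a level fixed in advance, set against 71%. A two-sided 80% interval would match the one-sided 10%, and section 14.2 already uses 80% and 90% intervals. Any statement about G-CLAM then rests on this interval and not on the pass rule, so (b) and (c) do not conflict at 34/41 or above. Note that 71% is treated as fixed, so that its own sampling error and patient similarity are not covered.

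Interim timing and power at 80% do not change. The cost is a less favourable set of stated operating characteristics, a narrower claim from a pass, and an interval about 19 points wide at 31/41 (84.3 − 64.9 = 19.4), which may leave 2.1.2 unresolved.

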14.0 STATISTICAL CONSIDERATIONS

14.1 General Considerations:

- 14.1.1 DLTs are defined in Section 8.3. Only DLTs occurring during Cycle 1 will be used to guide dose escalation.
- 14.1.2 Patients will be considered evaluable for DLT if they received at least 75% of the assigned decitabine and G-CLAM doses during Cycle 1 or if they developed a DLT. If a patient does not develop a DLT but does not receive at least 75% of treatment during Cycle 1, the patient will be considered not evaluable for DLT and will be replaced.
- 14.1.3 Maximum tolerated dose (MTD) is defined as the highest dose studied in which the incidence of DLT is <33%.

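### Section 14.3 sets the final DLT limit at 13 of 41 patients and labels it below 31%, but 13/41 is 31.7%, and nothing says which form governs

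*Combined protocol and SAP*

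**What the plan says.** Section 14.3 (Phase 2) describes a two-stage design with 19 patients in the first stage and 22 more in the second, 41 in total. It also counts patients from the dose-finding part: "Patients treated at the RP2D in Phase 1 will be included for assessment in Phase 2".

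DLTs are checked at two points:

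- **After 19 patients.** The study is suspended, and closure or dose reduction considered, "if 7 or more of the first 19 patients (36%) have what would qualify as a DLT in cycle 1". The reason given is "as we are targeting DLT <33% in Phase 1".
- **After 41 patients.** The regimen is judged worth pursuing if at least 31 patients reach MRDneg CR and "if 13 or fewer (<31%) have what would qualify as a DLT in cycle 1".

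Section 14.1.3 has a related threshold. It defines the MTD as "the highest dose studied in which the incidence of DLT is <33" percent. That figure is not stated to be the final Phase 2 criterion. The final DLT limit appears only once, in 14.3.

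**The concern.** A count with a percentage beside it should be one limit written two ways. Here the two forms give opposite answers at 13 DLTs, which is the boundary itself. A reader who applies the count passes the regimen on safety. A reader who applies the strict inequality fails it.

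This is the safety half of the final recommendation, and the limit is pre-specified so that nobody has to choose it after seeing the results. At exactly 13 DLTs, with enough responders, that choice would have to be made with the data known.

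**Working it through.** **Inputs from the plan.** Section 14.3: final DLT limit of 13, labelled below 31%; n = 41; stage 1 DLT limit (7 or more of 19 suspends, so 6 or fewer continues); response limits 13/19 and 31/41; null rate 65%, alternative 80%, historic G-CLAM rate 71%. Section 14.2: Phase 1 limits of at most 1 DLT in 6 and at most 3 in 12. Section 1.0 (rationale for the expansion cohort): 1 DLT in the first 6 newly diagnosed patients. The plan gives no expected DLT rate for the regimen, so true rates from 17% (1/6) to 33% are assumed below.

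**Step 1: the printed percentage.**

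| DLTs of 41 | Rate | At most 13? | Below 31%? |
|---|---|---|---|
| 12 | 29.3% | yes | yes |
| 13 | 31.7% | yes | **no** |
| 14 | 34.1% | no | no |

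The printed figure does not reproduce, and the forms disagree only at 13.

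**Step 2: could another denominator explain it?** 13/n < 0.31 needs n > 13/0.31 = 41.9, so n of at least 42 (13/42 = 30.95%). Section 14.3 fixes 41, and section 10.0 also gives 41 as the maximum treated at the MTD.

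**Step 3: the rest of the design.** The exact two-stage calculation (continue at 13/19, succeed at 31/41) gives a type-1 error of 0.096, power of 0.800 and early stopping under the null of 0.519. The plan states 10%, 80% and 51%. The response design therefore holds, and the problem is confined to the DLT bracket.

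**Step 4: how often the trial would end on 13 DLTs.** Let S(n) be the cumulative DLTs in the first n patients at the RP2D, independent with true rate p. The quantity is

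P[S(19) ≤ 6 and S(41) = 13, given S(6) ≤ 1 and S(12) ≤ 3],

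obtained by summing exact binomial probabilities over the increments of 6, 6, 7 and 22 patients. The second column of results instead fixes S(6) = 1, the reported value, assuming that all six patients count at the RP2D.

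| True DLT rate | 13 DLTs, Phase 1 limits met | Same, first six fixed at 1 DLT |
|---|---|---|
| 17% | 0.3% | 0.4% |
| 20% | 1.1% | 1.3% |
| 25% | 4.3% | 4.8% |
| 30% | 9.2% | 9.8% |
| 33% | 11.8% | 12.2% |

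**Step 5: how often the overall conclusion depends on it.** The response limits must also be met. That probability is 0.800, 0.309 or 0.096 at a true MRDneg CR rate of 80%, 71% or 65%. Multiplying the first results column by 0.800, with DLT and response assumed independent, gives 0.2%, 0.9%, 3.4%, 7.4% and 9.4%. At 71% the multiplier is 0.309: for example, 0.0109 × 0.309 = 0.3% at a DLT rate of 20%, and 0.0923 × 0.309 = 2.9% at 30%.

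**The case against.** The strongest reply is that the count is the rule and the bracket only describes it. Every Phase 2 limit in 14.3 is a count. The bracket in the stage 1 DLT rule is plainly a label, and it is also cut down: 7/19 = 36.8% is printed as 36%. Early stopping of 51.9% is printed as 51%. A truncated 31.7% would fit that habit. In addition, 13 is the largest count of 41 below the 33% target, and nothing in the plan supports 12 as the intended limit. This stands as the likely explanation. It is still an inference: the table in 14.2 rounds rather than truncates (2/12 = 16.7% is printed as 17%), and truncation does not explain the strict less-than sign, which the stage 1 bracket lacks.

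A second reply is that the sentence applies after all 41 patients have been evaluated, so it stops no accrual and changes nobody's treatment. That is correct, and it limits the consequence to the final recommendation.

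A third reply concerns the model. DLT and response are unlikely to be independent, because a DLT can be an early death or failed count recovery. If DLT patients responded at an assumed 40%, with the overall rate held at 80%, the 0.2% and 0.9% figures fall to about 0.1% and 0.5%, and the 7.4% figure at a DLT rate of 30% is nearly unchanged at 7.7%. The stage 1 DLT rule is also a suspension and not a certain stop. Ignoring it raises the 9.2% at a DLT rate of 30% to 10.2%. Neither point changes the picture.

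**Conclusion.** The error is real: as printed, the percentage excludes the count it is attached to, and no section says which one decides. Its reach is narrow. One outcome is affected, exactly 13 DLTs in 41, and the overall conclusion depends on it only when the response limits are also met.

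At a DLT rate near the 1 in 6 reported so far, a very small sample, this is well under 1% of trials. It reaches 7% to 9% only if the true DLT rate is 30% to 33% and the true MRDneg CR rate is 80%. These figures assume that the Phase 1 limits were met, patients are independent, and DLT is independent of response. The inconsistency itself rests on none of these assumptions. It should be corrected because it lies inside a pre-specified decision rule, although the probable intention can be guessed.

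**What to change.** Before the data are known, the sponsor should reconcile the count and the percentage in 14.3 so that both state the same limit. For reference, 13 of 41 is 31.7%, and strictly below 31% means at most 12 of 41 (29.3%). Which limit is intended is for the sponsor to say.

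The edit is to one bracket in one sentence. The type-1 error and power of the MRDneg CR test are the same either way. Keeping the count and correcting the percentage changes nothing else. Keeping the percentage and lowering the count to 12 makes the safety criterion stricter. Among trials that met the Phase 1 limits and had at most 6 DLTs in 19, the chance of meeting the final DLT criterion would be:

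| True DLT rate | At most 13 of 41 | At most 12 of 41 |
|---|---|---|
| 20% | 99% | 98% |
| 25% | 96% | 92% |
| 30% | 88% | 78% |
| 33% | 79% | 66% |

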15.0 ADMINISTRATIVE CONSIDERATIONS

16.1 Investigator obligations

The PI is responsible for the conduct of the clinical trial and is responsible for overseeing the treatment of all study subjects. The PI must assure that all study personnel adhere to the study protocol and guidelines regarding clinical trials both during and after study completion. The PI assumes the responsibility of ensuring that all patients have given their informed consent prior to study enrollment.

16.2 Documentation

The PI and study staff are responsible for maintaining a comprehensive filing system containing study related documentation, including signed informed consents for each subject. The files must be suitable for inspection by regulatory agencies at any time.

16.3 Ethical considerations

The Investigator agrees to conduct this study in accordance with applicable United States FDA clinical trial regulations and guidelines, applicable United States FDA clinical trial regulations and guidelines, the ICH (E6) GCP guidelines, the European Union Directive 2001/20/EC for clinical trials conducted in the European Union, the IRB/EC and local legal requirements and with the Declaration of Helsinki (1989). The Investigator will conduct all aspects of this study in accordance with all national, state, and local laws of the applicable regulatory agencies.

16.3 Informed consent

Subjects meeting the criteria set forth in the protocol may be offered the opportunity to participate in the study. Subjects will receive a comprehensive explanation of the proposed treatment, including the nature of the therapy, alternative therapies available, any known previously experienced adverse reactions, the investigational status of the study drug, and other factors that are part of obtaining a proper Informed Consent. Subjects will be given the opportunity to ask questions concerning the study, and adequate time to consider their decision to or not to participate. Informed Consent will be documented by the use of a written Consent Form that includes all the elements required by FDA regulations and ICH guidelines. A copy of the signed form will be given to the person who signed it, the original signed Consent Form will be filed with the subject's medical records, and copy maintained with the subject's study records. The date and time of time of the Informed Consent must be recorded in the source documents.

